9.4.3.8 Continuous and Spot End Tidal Carbon Dioxide

The spot end tidal CO₂ levels and change from baseline (day 9) will be listed and summarized by treatment group and time point. The number and percentage of participants with end tidal CO₂ levels as per **Table 10** at any time point will be summarized by treatment group. The lowest and the highest end tidal CO₂ level, respectively, will be used in the analysis.

Table 10 Criteria for Assessing Spot End Tidal Carbon Dioxide

Parameter	Criteria
End Tidal CO ₂ (mmHg)	< 20, < 25, < 30, < 35 > 35, > 40, > 45, > 50

CO₂: carbon dioxide

The number and percentage of participants who reach an alarm value of continuous end tidal CO₂, and the number of times an alarm value was reached will be listed and summarized by treatment.

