3. Participants will be discharged from the clinical unit on day 16 on the condition that all required assessments have been performed and that there are no medical reasons for a longer stay in the clinical unit. If a participant discontinues early from the study, discharge/ESV procedures will be performed upon discontinuation.
4. The ESV will take place 5 to 9 days after the day 16 pharmacokinetic sample is collected or at early discontinuation/termination from the study.
5. Randomization can occur on day -1 or predose on day 1 provided that eligibility is confirmed prior to randomization.
6. TLFB will be collected for 2 weeks prior to screening or on day -1 (prior to any assessments).
7. Height to be collected at screening only.
8. Clinical laboratory tests include blood collection for serology (at screening only), hematology and biochemistry and urine collection for urinalysis.
9. Serum pregnancy test at screening and urine pregnancy test on day -1 and at the ESV.
10. Vital signs include measurements of blood pressure, pulse, respiratory rate and oral temperature. Measurements will be taken after the participant has been resting in the supine position for at least 5 minutes. Measurements will be taken in duplicate at screening and on day -1 and at all other time points as single measurements.

Footnotes continued on next page

11. Continuous pulse oximetry will begin predose on days 9 and 10 until at least 8 hours postdose..
12. 12-lead ECGs will be taken after the participant has been resting in the supine position for at least 5 minutes. 12-lead ECGs will be taken in triplicate.
13. Symptom-directed physical examinations may be performed on days 9 and 16. Full physical examinations will be performed at screening, day -1 and ESV.
14. Single SpO₂ measurements will be taken at designated time points.
15. The version of the C-SSRS to be performed at screening is the “Baseline/Screening” and the version of the C-SSRS to be performed on days -1, 9 and 16 and at the ESV is the “Since Last Visit”.
16. Continuous and spot end tidal CO₂ to be collected starting predose on days 9 and 10 until 8 hours postdose. Time points will be recorded predose and 1, 2, 4 and 8 hours postdose. The cannula may be removed while participants dose or eat.
17. The blood sample for biomarker and PGx analysis (biobanking) can be collected on day -1 or predose on day 1.

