18. On days 1, 9 and 10, ASP8062 or placebo will be administered orally under fasting conditions (i.e., no food or beverage will be allowed from at least 10 hours predose through at least 4 hours postdose) with approximately 240 mL water. Water intake will be prohibited from at least 1 hour predose through at least 1 hour postdose, except for the approximately 240 mL water to swallow the investigational product. On all other dosing days, ASP8062 or placebo will be administered orally under standardized fed conditions (i.e., meals will be served up to 1 hour predose or at least 2 hours postdose) with approximately 240 mL water. Water intake will be allowed ad libitum.
19. On day 10, morphine will be administered as a single oral dose under existing fasting conditions with approximately 240 mL water, immediately after the ASP8062 or placebo dose. Water intake will be prohibited from at least 1 hour predose through at least 1 hour postdose, except for the approximately 240 mL water to swallow the investigational product.

Table 2 Sample Collection Schedule

Day	Time Point	Pharmacokinetics ASP8062/metabolites	Pharmacokinetics Morphine/metabolites	Vital Signs	Clinical Laboratory Tests	12-lead ECG	ARCI-49	Spot End Tidal CO ₂	Spot SpO ₂
Days -28 to -2	Screening			X	X	X			
-1				X	X	X			
1	Predose			X	X	X	X		X
	2 hours								
2	Predose								
	2 hours								
3	Predose			X	X				
	2 hours								
4	Predose								
	2 hours								
5	Predose								
	2 hours								
6	Predose			X	X				
	2 hours								
7	Predose								
	2 hours								
8	Predose								
	2 hours								

Table continued on next page

Day	Time Point	Pharmacokinetics ASP8062/metabolites	Pharmacokinetics Morphine/metabolites	Vital Signs	Clinical Laboratory Tests	12-lead ECG	ARCI-49	Spot End Tidal CO ₂	Spot SpO ₂
9	Predose	X		X	X	X	X	X	X
	0.25 hour	X							
	0.5 hour	X							
	1 hour	X		X				X	X
	1.5 hours	X							
	2 hours	X		X	X	X	X	X	X
	2.5 hours	X							
	3 hours	X							
	4 hours	X		X		X	X	X	X
	6 hours	X							
	8 hours	X		X			X	X	X
	12 hours	X		X		X	X		X
	16 hours	X							
10	Predose	X	X	X	X	X	X	X	X
	0.25 hour	X	X						
	0.5 hour	X	X						
	1 hour	X	X	X				X	X
	1.5 hours	X	X						
	2 hours	X	X	X	X	X	X	X	X
	2.5 hours	X							
	3 hours	X	X						
	4 hours	X	X	X		X	X	X	X

Table continued on next page

Day	Time Point	Pharmacokinetics ASP8062/metabolites	Pharmacokinetics Morphine/metabolites	Vital Signs	Clinical Laboratory Tests	12-lead ECG	ARCI-49	Spot End Tidal CO ₂	Spot SpO ₂
10	6 hours	X							

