2 INTRODUCTION

2.1 Study Rationale

An in vitro cytochrome P450 (CYP) identification study suggested that ASP8062 is mainly metabolized by CYP3A4, while morphine shows no inhibitory effect on CYP3A in an in vitro study [Haaz et al, 1998]. Morphine is metabolized by multiple UDP-glucuronosyltransferases [De Gregori et al, 2012; Sato et al, 2012; Court et al, 2003; Projean et al, 2003]. Therefore, the pharmacokinetic drug-drug interaction (DDI) potential of ASP8062 with opioids is considered to be low. Potential interaction such as opioid effects on respiratory depression is theoretically possible because both ASP8062 and opioids are centrally active [Pattinson, 2008].

For future studies in opioid use disorder (OUD) patients, ASP8062 will be coadministered with opioids, including standard medication-assisted treatments such as buprenorphine/naloxone. Among opioid receptors, the μ -receptor is considered to play a role in the decrease in the respiratory response to hypoxia, resulting in a decreased stimulus to breathe and the development of apnea [Schiller & Mechanic, 2019]. ASP8062 has not been observed to directly interact with opioid receptor [study 8062-PH-9005] and the preclinical DDI study [study 8062-PH-9055] between ASP8062 and morphine, a full agonist for opioid μ -receptor, failed to find any pharmacodynamic (i.e., respiratory depression) interaction including general condition. This clinical DDI/safety study will provide relevant safety (particularly for respiratory depression), tolerability and pharmacokinetic data in order to assess the potential risk of ASP8062 coadministered with morphine, a full agonist for opioid μ -receptor to support future studies in this patient population. The study was designed particularly to investigate if ASP8062 has any additive effect on top of morphine by instituting the sensitive measure of end tidal carbon dioxide (CO_2), using a single morphine dose slightly above the highest approved individual morphine dose, but presumably still allowing room to detect potential additive effects of ASP8062.

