3 OBJECTIVES, ENDPOINTS AND ESTIMANDS

Table 3 Study Objectives and Endpoints

Objectives	Endpoints
Primary	
• To assess the safety and tolerability of multiple doses of ASP8062 or placebo alone and in combination with a single dose of morphine• Nature, frequency and severity of AEs• Clinical laboratory tests (hematology, biochemistry and urinalysis)• Vital signs (blood pressure, pulse and respiratory rate)• 12-lead ECG• C-SSRS• SpO₂• End tidal CO₂
Secondary	
• To assess the potential for pharmacokinetic interaction between ASP8062 and morphine• Plasma ASP8062: AUC₂₄ and C_{max}• Plasma morphine and its metabolites (M3G and M6G): AUC_{inf}, AUC_{last} and C_{max}
Exploratory	
• To assess additional safety and tolerability of multiple doses of ASP8062 or placebo alone and in combination with a single dose of morphine• Oral temperature• ARCI-49• To assess the general pharmacokinetic parameters of ASP8062, its metabolites, morphine and its metabolites• Plasma ASP8062: CL/F, t_{1/2}, t_{max}, t_{lag}, V_z/F, C_{trough} and PTR• Plasma ASP8062 metabolites (AS3486189, AS3486191 and AS3486192): C_{max}, AUC₂₄, t_{1/2}, t_{max}, t_{lag}, V_z/F, C_{trough} and PTR• Plasma morphine and its metabolites (M3G and M6G): AUC_{inf}(%extrap), CL/F (morphine), t_{1/2}, t_{max}, t_{lag} and V_z/F• Plasma ASP8062 metabolites (AS3486189, AS3486191 and AS3486192): AUC₂₄ and C_{max}

AE: adverse event; ARCI-49: 49-item short form of Addiction Research Center Inventory scale; CO₂: carbon dioxide; C-SSRS: Columbia-suicide severity rating scale; ECG: electrocardiogram; M3G: morphine-3β-D-glucuronide; M6G: morphine-6β-D-glucuronide; SpO₂: blood oxygen saturation

Estimands

Not applicable.

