9.4.3.4 Continuous Pulse Oximetry and Spot Blood Oxygen Saturation

The spot SpO₂ levels and change from baseline (day 1) will be listed and summarized by treatment group and time point. The number and percentage of participants with SpO₂ levels

as per [Table 8] at any time point will be summarized by treatment group. The lowest SpO₂ level across the time points will be used in the analysis.

Table 8 Criteria for Assessing Spot Blood Oxygen Saturation

Parameter	Criteria
SpO ₂ level (%)	< 90, < 92, < 94, < 96

SpO₂: blood oxygen saturation

The number and percentage of participants who reach an alarm value of continuous pulse oximetry, and the number of times an alarm value was reached will be listed and summarized by treatment.

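### End tidal CO₂: the plan gives no between-arm difference or interval for the additive question the study was built around, and it does not say which day 9 reading is the baseline

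*Combined protocol and SAP*

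**What the plan says.** Section 2.1 states the aim: "The study was designed particularly to investigate if ASP8062 has any additive effect on top of morphine", with end tidal CO₂ as the sensitive measure. Table 3 in section 3 lists end tidal CO₂ under the primary objective: "To assess the safety and tolerability of multiple doses of ASP8062 or placebo alone and in combination with a single dose of morphine".

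The analysis is in section 9.4.3.8: "The spot end tidal CO₂ levels and change from baseline (day 9) will be listed and summarized by treatment group and time point". That section adds counts of participants crossing the Table 10 limits, based on each participant's lowest and highest value, and counts of alarms from continuous monitoring. Section 9.4.3 defines four groups: each randomised arm alone and each arm with morphine. Sections 9.1 and 9.2 declare no hypotheses and no power.

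Footnote 16 to Table 1 fixes the collection: "Continuous and spot end tidal CO₂ to be collected starting predose on days 9 and 10 until 8 hours postdose", and "Time points will be recorded predose and 1, 2, 4 and 8 hours postdose". Table 2 schedules no end tidal CO₂ before day 9. Spot SpO₂ does have a day 1 predose reading, and section 9.4.3.4 uses day 1: "The spot SpO₂ levels and change from baseline (day 1) will be listed and summarized by treatment group and time point".

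Section 9.4.4.3 compares the two morphine groups on log-transformed exposure to morphine and its glucuronides. It does so by analogy with the ASP8062 analysis, which reports geometric mean ratios with 90% CIs.

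**The concern.** An additive effect on top of morphine is a comparison of two randomised groups on day 10. The plan shows each group's CO₂ separately and never forms the comparison. With about 16 and 8 participants, two similar-looking columns of means could be taken as reassurance when the data are compatible with a sizeable difference. An interval is what guards against that reading. The pharmacokinetic section shows that the sponsor accepts interval estimates between these same arms in an unpowered study.

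The second issue is the change score. The reference is given only as day 9, which has five spot readings. The general rule in section 9.4.1 (last value before first dosing) cannot supply the answer, because no CO₂ is measured that early. By day 9 the ASP8062 arm has taken eight or nine doses of a drug with a half-life of about 60 hours, while the placebo arm has had none. A reader who compares change scores across arms would therefore subtract an on-drug value in one arm and a drug-free value in the other. The neighbouring SpO₂ table, with its day 1 reference, answers a different question under the same column label.

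**Working it through.** The plan has no precision figure for end tidal CO₂ to reproduce; the only precision statement (section 9.2) concerns pharmacokinetics.

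**1. What each contrast estimates.** Let A9 and A10 be the effect of ASP8062 alone on each day, and I any interaction with morphine on day 10.
- Between-arm difference in day 10 level = A10 + I, the total ASP8062 effect in the presence of morphine.
- Between-arm difference in change from day 9 = A10 + I − A9.

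Illustration with assumed effects: ASP8062 adds 2 mmHg on both days, morphine adds 5 mmHg, and there is no interaction. The level difference is 7 − 5 = 2. The time-matched change difference is (7 − 2) − (5 − 0) = 0. Using day 9 as a covariate meets the same difficulty, because it is a post-randomisation, on-drug value in one arm.

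**2. Precision of the level difference.** Inputs: 24 enrolled and at least 18 completing (section 9.2), allocated 2:1 (section 6.3.6.2). That gives 16 v 8, or 12 v 6 if completers keep the ratio. The 90% half-width is t(0.95, n1+n2−2) × √(1/n1 + 1/n2) × SD.
- 16 v 8: 1.717 × 0.433 = 0.74 SD.
- 12 v 6: 1.746 × 0.500 = 0.87 SD.
- At an assumed SD of 3 to 5 mmHg: 2.2 to 3.7 mmHg (16 v 8) and 2.6 to 4.4 mmHg (12 v 6).

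For a change score, multiply by √(2(1−ρ)), with equal SDs on both days. At 16 v 8 this gives 0.88, 0.74, 0.58 and 0.47 SD for ρ = 0.3, 0.5, 0.7 and 0.8. Change is tighter above ρ = 0.5, but it estimates a different quantity.

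**3. How much a between-arm change contrast would remove.** Assume the effect is proportional to ASP8062 concentration, and express the amount removed as a share of the ASP8062-alone effect on the day 10 mean over 1, 2, 4 and 8 h. Inputs: half-life about 60 h (section 4.2); predicted AUC₂₄ 1828 h·ng/mL and Cmax 143 ng/mL (section 4.3). Daily retention is r = 2^(−24/60) = 0.758.
- *Time-matched day 9 baseline:* (1 − r⁹)/(1 − r¹⁰) = 0.9175/0.9375 = 0.979, about 98%.
- *Predose day 9 baseline:* accumulation alone gives (1 − r⁸)/(1 − r¹⁰) = 0.8912/0.9375 = 0.951. That would be the share removed only if the concentration profile were flat over the day. Here Cmax/average = 143/(1828/24) = 143/76.2 = 1.88, and a one-phase profile with this half-life cannot exceed 0.277/(1 − 0.758) = 1.145. A two-phase profile is needed.

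Take C(t) = A·e^(−αt) + B·e^(−βt) − (A+B)·e^(−kt), summed over doses, with β = ln2/60 and A/B chosen to give 1.88 on day 10. Example: first-phase half-life 4 h and k = 2 per h require A/B = 7.9. In units of B:
- Day 9 predose: 0.758 × 0.8912/0.2421 + 7.9 × 0.0159 = 2.79 + 0.13 = 2.92.
- Day 10 at 1, 2, 4 and 8 h: 9.37, 9.30, 7.71 and 5.54; mean 7.98.
- Ratio: 2.92/7.98 = 0.37.

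First-phase half-lives of 2 to 8 h and k of 1 to 4 per h (all assumed) give roughly 20% to 60%.

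For an assumed ASP8062-alone effect of 2 mmHg, the shift is about 2.0 mmHg time-matched (2 × 0.979) and about 0.4 to 1.2 mmHg predose (2 × 0.2 to 2 × 0.6). It is zero if there is no such effect. These ratios ignore the dosing-condition change before day 9: days 9 and 10 are fasted, but "On all other dosing days, ASP8062 or placebo will be administered orally under standardized fed conditions".

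**The case against.** The study is openly descriptive. It has no hypotheses and no power, and no safety endpoint in section 9.4.3 gets a contrast, so a pharmacokinetic interval does not by itself create a duty to give one here. Absolute levels are summarised for both morphine groups at every time point and listed individually, so a reader can subtract the means. Change from day 9 is a sensible within-arm description of what morphine adds, predose is the natural reading of the baseline, and no pre-drug CO₂ was available to use.

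Much of this stands. The difference can be derived from the planned output, and nothing planned is invalid. But subtracting means gives four unprioritised differences. By-time-point summaries cannot give an interval for a participant-level mean, because that needs the within-participant covariance. Working from listings would be post hoc. Being unpowered argues against a test and does not argue against an estimate with an interval.

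Two stronger readings are tempting and are not supported. A reader might infer that a predose day 9 baseline would remove about 95% of the ASP8062 effect. That needs a nearly flat concentration profile, which the Cmax and AUC₂₄ in section 4.3 contradict. A reader might also infer that the planned CO₂ analysis is biased. Section 9.4.3.8 does not compare change scores between arms, so the distortion arises only if someone makes that comparison.

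**Conclusion.** The main point holds: for the question the study was particularly designed to address, on a primary endpoint, the plan offers no between-arm estimate and no interval. The arithmetic on precision rests only on the planned numbers and the 2:1 ratio; the conversion to mmHg rests on an assumed SD.

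The baseline point is secondary and conditional. The reading is unnamed, and it is on drug in one arm only. If change scores were compared between arms, the total effect would be understated where ASP8062 alone raises CO₂ and overstated where it lowers CO₂. The documents do not give the sign. The share removed (about 98% time-matched, roughly 20% to 60% predose) depends on the proportionality and profile assumptions above. Levels, threshold counts and alarm counts are untouched. This is a cheap improvement and does not show a flaw in the design.

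**What to change.** 1. In section 9.4.3.8, pre-specify the day 10 difference in end tidal CO₂ level between ASP8062 plus morphine and placebo plus morphine, with a 90% CI. Use one per-participant summary chosen in advance, for example the mean over 1, 2, 4 and 8 h, and label it estimation and not a powered test. Give the same difference for day 9 as the ASP8062-alone effect.
2. Name the day 9 reading that serves as baseline, for example predose. Footnote that it is on drug in the ASP8062 arm, unlike the day 1 reference for SpO₂. State that change from day 9 describes what happens within an arm and is not the basis for statements about ASP8062 versus placebo.

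The cost is protocol or SAP wording, one footnote and a few table rows, from data already scheduled; no procedure changes. The downside is wide intervals, and levels are less precise than change scores if the within-participant correlation exceeds 0.5. The text should say that an interval including zero does not show the absence of an additive effect.

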9.4.4 Analysis of Pharmacokinetics

Descriptive statistics will include n, mean, SD, minimum, median, maximum, CV, geometric mean and geometric CV. For the pharmacokinetic parameters t_{max} and t_{lag} , only n, median, minimum and maximum will be calculated.

9.4.4.1 Pharmacokinetic Concentrations

Descriptive statistics will be presented for plasma concentrations of morphine and its metabolites (M3G and M6G) in combination with placebo and in combination with ASP8062 by scheduled sample time. Standard graphics including mean plasma concentration-time profiles, overlay (spaghetti) plots and individual participant plasma concentration-time profiles for morphine and its metabolites (M3G and M6G) in combination with placebo and in combination with ASP8062 will be produced.

Descriptive statistics will be presented for plasma concentrations of ASP8062 and its metabolites (including AS3486189, AS3486191 and AS3486192) alone and ASP8062 in combination with morphine by scheduled sample time. Standard graphics including mean plasma concentration-time profiles, overlay (spaghetti) plots and individual participant plasma concentration-time profiles for ASP8062 and its metabolites (including AS3486189, AS3486191 and AS3486192) alone and ASP8062 in combination with morphine will be produced.

9.4.4.2 Estimation of Pharmacokinetic Parameters

Noncompartmental analysis will be used for the calculation of plasma pharmacokinetic parameters using Phoenix version 6.3 or higher (Certara LP, 100 Overlook Center, Suite 101, Princeton, NJ 08540, US).

Plasma pharmacokinetic parameters of morphine and its metabolites (M3G and M6G) in combination with placebo and in combination with ASP8062 will be listed and summarized using descriptive statistics.

Plasma pharmacokinetic parameters of ASP8062 and its metabolites (including AS3486189, AS3486191 and AS3486192) alone and ASP8062 in combination with morphine will be listed and summarized using descriptive statistics.

9.4.4.3 Statistical Analysis of Pharmacokinetic Parameters

To assess the effect of morphine on the pharmacokinetics of ASP8062 and its metabolites (AS3486189, AS3486191 and AS3486192), an analysis of variance (ANOVA) model with treatment (ASP8062 in combination with morphine and ASP8062 alone) as a fixed effect and participants as a random effect will be fitted on natural logarithmic-transformed AUC_{24} and C_{max} . Within the ANOVA, the least squares (LS) mean differences between ASP8062 in combination with morphine and ASP8062 alone, along with 90% CIs for the differences will be estimated. The LS means for AUC_{24} and C_{max} will be back-transformed to produce the geometric LS means and presented with the number of participants for each treatment. The geometric LS mean ratios and their corresponding 90% CIs for each pharmacokinetic parameter will be presented by back-transforming and expressed as percentages.

To assess the effect of ASP8062 on the pharmacokinetics of morphine and its metabolites (M3G and M6G), similar analysis will be done with treatment (morphine in combination with ASP8062 and morphine in combination with placebo) as a fixed effect and participant as a random effect.

If all participants did not complete treatment, then the above analyses will be repeated using an ANOVA with fixed effects for treatment and participant; this analysis will only include participants with complete data in all treatments.

9.4.5 Other Analyses

Select polymorphisms of genes GABA_B receptor and/or opioid receptors will be summarized and listed. In addition, polymorphisms of genes may be summarized graphically or descriptively as they relate to clinical measures, as applicable. All analyses described in this section are based on availability of data.

9.5 Interim Analysis

Not applicable.

9.6 Additional Conventions

As a general principle, no imputation of missing data will be done. Exceptions are the start and stop dates of AEs and concomitant medications if they are missing on day of first IP administration. The imputed dates will be used to assess if the AEs or concomitant medications are treatment-emergent or concomitant, respectively. Listings of the AEs and concomitant medications will present the actual partial dates; imputed dates will not be shown.

